### 6.8.3.6 Relationship between SCD-044 plasma concentrations and efficacy/PD endpoints

11. **What is the primary purpose of the *Journal of Clinical Endocrinology and Metabolism*?**

11. **What is the primary purpose of the *Journal of Clinical Endocrinology and Metabolism*?**

## 6.9 Pharmacokinetic Analyses

11. **What is the primary purpose of the *Journal of Clinical Endocrinology and Metabolism*?**

In addition, PK sample will be collected, if possible, approximately 1 hour within the onset of an AE related to bradycardia during the [REDACTED] monitoring.

PK concentrations will be summarized descriptively by visit, timepoint and treatment group, including CV%, geometric mean and geometric CV%.

Concentrations reported as below limit of quantification (BLQ) will be treated as 0 for the purposes of the summary if they precede quantifiable samples prior to the first measurable concentration or occur after the last quantifiable concentration. A BLQ concentration embedded between two quantifiable concentrations during the post-dose collections on Day 29 will be set to missing. Missing values will not be imputed.

PK parameters will be estimated using noncompartmental analysis with the software program WinNonLin version 8.4 or higher for subjects who had PK samples collected from pre-dose to 6 hours post-dose on Day 29 under protocol version 2. The parameters will include:

- maximum concentration ( $C_{max}$ )
- time to maximum concentration ( $t_{max}$ )
- Area under the concentration-time curve up to 6 hours ( $AUC_{0-6}$ )
- Area under the concentration-time curve up to the last observed quantifiable concentration ( $AUC_{0-last}$ ).

Pharmacokinetic parameters will be summarized descriptively by treatment group. However, PK parameters from subjects with emesis occurred within 5 hours post-dose on Day 29 will not be included into descriptive statistics.

## 6.10 Analyses of PD biomarkers

[REDACTED] blood sample will be collected for testing of:

- Cytokines in plasma/serum: [REDACTED]
- Cell types in blood:  
[REDACTED]  
[REDACTED]  
[REDACTED]  
[REDACTED]  
[REDACTED]  
[REDACTED]

Additional biomarkers may be included during the study.

## **6.11 Safety Analyses**

All safety analyses will be performed on the Safety population.

### **6.11.1 Adverse Events**

Adverse events will be coded using MedDRA, Version 25.0, AE coding system for purposes of summarization.

An AE will be considered as treatment-emergent (TEAE) if the date of onset is on or after the date of the first study drug administration. AEs with unknown start dates will be counted as treatment-emergent unless the AE resolution date is prior to the study drug start date. If the start date is partially missing, the AE will be considered treatment-emergent, unless the month and year (when available) rule out the possibility that the event occurred post start of study drug dosing.

A TEAE is defined as treatment-related if its relationship to study medication is recorded as “Possible”, “Probable” or “Definite” on the eCRF. In case the relatedness was not assessed, the most conservative result (related) will be chosen for the analysis.

Cardiovascular AEs will be defined as AEs with MedDRA system organ class “Cardiac disorders” or “Vascular disorders”.

Adverse events that are of special interest, that represent signs/symptoms of Progressive Multifocal Leukoencephalopathy (PML) or of Posterior Reversible Encephalopathy Syndrome (PRES) and that are cardiac arrhythmias will be marked on the eCRF.

AEs will be assigned to Part I or Parts II/III of the study based on the date of onset, i.e. AEs that start prior to the first dose of the Part II treatment will be assigned to the Part I and AEs that start on or after the date of the first Part II dose will be assigned to the Parts II/III. In case AE start date is partially known so that there exists an ambiguity whether the AE starts in Part I or Part II, it will be assigned to Part I.

In summaries of TEAEs a subject experiencing the same AE multiple times on the same treatment will only be counted once for that preferred term and treatment. Similarly, if a subject experiences multiple AEs within the same system organ class on the same treatment that subject will be counted only once in that system organ class and treatment. When summarizing AEs by severity, only the most severe occurrence within the preferred term or system organ class and treatment will be used. Similarly, when summarizing AEs by relationship to study drug, only the most related occurrence within the preferred term or system organ class and treatment will be selected for displays in summary tables.

All AE summaries will be presented in 3 ways:

1. For events in Part I only, using Part I treatment groups, with the additional groups SCD-044 Any Dose (including the three SCD-044 groups) and Total (including all subjects).
2. For events in Parts II/III/IV only, using Parts II/III/IV safety treatment groups, with the additional group Total.

3. For the entire study using only the subjects who stayed on the same treatment throughout the study, using the three active treatment groups with the additional group Total.

An overall summary for the Safety population will include, by treatment and overall, the number and percentage of subjects reporting at least 1 TEAE in the following categories:

- Any TEAE
- Treatment-related TEAE
- Serious TEAE
- Serious drug-related TEAE
- TEAE leading to discontinuation of the study medication
- Treatment-related TEAE leading to discontinuation of the study medication
- TEAE requiring temporary interruption of the study medication
- Treatment-related TEAE requiring temporary interruption of the study medication
- TEAE leading to death.
- TEAEs of special interest

Additional overall summary of cardiovascular TEAEs will include, by treatment and overall, the number and percentage of subjects reporting at least one cardiovascular TEAE in the following categories:

- Any cardiovascular TEAE
- Treatment-related cardiovascular TEAE
- Serious cardiovascular TEAE
- Cardiovascular TEAE leading to discontinuation of the study medication
- Cardiovascular TEAE leading to death.
- Cardiovascular TEAEs of special interest
- Cardiac arrhythmias

The following TEAE frequency tables will be prepared summarizing the number and percentage of subjects reporting at least one TEAE by MedDRA System Organ Class (SOC) and preferred term PT, by treatment group for the Safety population:

- All TEAEs
- Serious TEAEs
- Treatment-related TEAEs
- Serious treatment-related TEAEs
- TEAEs leading to discontinuation of the study medication
- Treatment-related TEAEs leading to discontinuation of the study medication
- TEAE requiring temporary interruption of the study medication
- Treatment-related TEAE requiring temporary interruption of the study medication
- TEAEs occurring in  $\geq 2\%$  in any treatment group
- TEAEs of special interest
- Cardiac arrhythmias
- TEAEs with onset during the [REDACTED] period in Part I and in Part II
- TEAEs by Severity

- TEAEs by Relationship to Study Drug.

The tables for the [REDACTED] periods will be separated into sections for Week 1, Week 2 and Week 3 of [REDACTED] where the weeks are defined by the dates of the [REDACTED] visits (Week 1, Week 2 and Week 3 for Part I and Week 16, Week 17 and Week 18 for Part II). Only events occurring in each week in the treatment groups still undergoing [REDACTED] (including the Placebo group in Part I) will be included. In the Part II table five columns will be included: Placebo/SCD-044 [REDACTED] Placebo/SCD-044 [REDACTED] SCD-044 [REDACTED] SCD-044 [REDACTED] and Total as only these groups actually undergo [REDACTED] in Part II.

All information pertaining to adverse events noted during the study will be listed by subject, detailing verbatim, preferred term, system organ class, start date and study day, stop date, intensity, outcome, action taken and causal relationship to the study drug. The adverse event onset will also be shown relative (in number of days) to the date of first administration of the study drug.

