4.6 Precautions

The following precautions are to be taken during this study:

- [REDACTED]
[REDACTED]
- [REDACTED]
[REDACTED]
[REDACTED]
[REDACTED]
[REDACTED]
[REDACTED]
[REDACTED]
[REDACTED]
[REDACTED]
[REDACTED]

The therapeutic class of S1P agonists carries following known and/or potential risks:

- Bradyarrhythmia and atrioventricular conduction delays
- Hypotension
- Increased blood pressure
- Increased risk of infections
- Macular edema
- Decline in pulmonary function
- Liver injury
- Progressive multifocal leukoencephalopathy (PML)
- Posterior reversible encephalopathy syndrome (PRES)

If an adverse reaction suggesting Subject's condition has worsened to the degree that it is unsafe for the Subject to continue in the study, the Principal Investigator should assess the Subject's condition as soon as possible (i.e., during an Unscheduled Visit) and determine whether treatment should be

discontinued. If the Subject is discontinued from the study during an Unscheduled Visit, procedures from Early Discontinuation should be followed and the visit will be referred to as an Early Discontinuation Visit.

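### The cardiovascular TEAE summary rests on two MedDRA system organ classes alone, so a heart-rate, blood-pressure or ECG event coded elsewhere is left out, and it is unclear how eCRF-marked arrhythmias enter it

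*SAP*

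**What the plan says.** SAP section 6.11.1 names the dictionary: "Adverse events will be coded using MedDRA, Version 25.0". It then sets the grouping rule: "Cardiovascular AEs will be defined as AEs with MedDRA system organ class" Cardiac disorders or Vascular disorders. The public text adds no preferred-term list and no standardised query.

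Arrhythmias are identified by a different route. The same section says that events of several kinds, "and that are cardiac arrhythmias will be marked on the eCRF".

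The grouping feeds one table: "Additional overall summary of cardiovascular TEAEs will include, by treatment and overall, the number and percentage of subjects reporting at least one cardiovascular TEAE". Its rows are any, treatment-related, serious, leading to discontinuation, leading to death, of special interest, and cardiac arrhythmias. Cardiac arrhythmias appear again in section 6.11.1 as a separate frequency table by system organ class (SOC) and preferred term.

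Protocol section 4.6 lists the risks of the drug class. They include "Bradyarrhythmia and atrioventricular conduction delays", hypotension, and "Increased blood pressure".

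**The concern.** The class risks concern heart rate, cardiac conduction and blood pressure. The trial looks for them by measurement: Protocol sections 5.3 and 5.12 prescribe pulse, blood pressure and ECG readings. Protocol section 5.9 lets signs and clinically significant abnormal laboratory results be reported as adverse events, not only diagnoses. It is therefore foreseeable that a site will describe an event as a measured finding instead of a diagnosis.

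A rule based on SOC alone makes the pooled count depend on that wording. A slow pulse coded as a cardiac disorder is counted. The same slow pulse coded as a test finding under another SOC is not. The cardiovascular summary is the one listed adverse-event table that pools cardiovascular events by relatedness, seriousness and discontinuation for each treatment group. In a dose-ranging study, the pattern across doses is what a reader will look for in it.

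The arrhythmia row raises a second question. It sits in a table restricted to cardiovascular TEAEs, but arrhythmias are identified by the eCRF mark and not by SOC. The SAP does not say which rule governs the row.

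**Working it through.** The plan gives no expected event rate by SOC, so there is no planned figure to reproduce. The check is to trace how events pass through the rules in SAP section 6.11.1.

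**Step 1: routing.** The main rows are any, related, serious, discontinuation and death.

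| Event as coded | Arrhythmia mark | Main cardiovascular rows | Arrhythmia row of that summary | Separate arrhythmia table |
|---|---|---|---|---|
| Slow heart rate, Cardiac disorders | yes | counted where it qualifies | counted | counted |
| Slow heart rate, another SOC | yes | not counted | unclear | counted |
| ECG finding that is not an arrhythmia, another SOC | no | not counted | not counted | not counted |
| Low or raised blood pressure, Vascular disorders | no | counted where it qualifies | not counted | not counted |
| Low or raised blood pressure, another SOC | no | not counted | not counted | not counted |

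The second row shows the ambiguity about the mark. The third and fifth rows show events with no alternative route into the pooled summary, because the visible text provides a mark for arrhythmias but none for blood pressure or other ECG findings. The special-interest row gives no way round this, because it too is limited to cardiovascular events.

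**Step 2: direction.** The wider definition adds events to the two SOCs and removes none. For each row, the count under the present rule is therefore less than or equal to the count under the wider one. A subject is lost from a row only if no other event in the two SOCs qualifies that subject for the same row on the same treatment.

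**Step 3: scale.** The protocol synopsis plans about 240 subjects at 1:1:1:1.

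- Planned Part I arm: 240 / 4 = 60.
- One missed subject: 1 / 60 = 1.7 percentage points.
- Two missed: 2 / 60 = 3.3 points. Three missed: 3 / 60 = 5.0 points.

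Purely as an illustration, assume that 6 of 60 subjects in an arm have a heart-rate or ECG adverse event and no other qualifying event. If all are coded within the two SOCs, the table shows 6 / 60 = 10%. If half are coded elsewhere, it shows 3 / 60 = 5%. If all are coded elsewhere, it shows 0%. Neither the 6 nor the split comes from the documents. The summaries for Parts II to IV, and for subjects who stay on one treatment throughout, have other denominators.

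**The case against.** The strongest reply is that little is lost. The SAP calls this table additional, and the same risks are covered in several other places:

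- the separate arrhythmia table, which no reading ties to the two SOCs
- pulse-rate thresholds of 40 and 50 bpm and the ECG results, which use measured values and do not depend on site wording
- the summary of subjects who need monitoring beyond 6 hours, with reasons
- the interim cardiac analysis and the DSMB cardiac review (SAP sections 7.1 and 7.2)
- the TEAE tables by SOC and preferred term, and the full listings

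Safety is descriptive, since Protocol section 9.7 plans no inferential analyses, so no error rate or power depends on the grouping. Neither document reproduces the MedDRA hierarchy. Parts of the vital-sign and ECG sections and one event of special interest are missing from the public copy, and the table shells are a separate document that may hold a term list.

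Most of this stands, and it sets the limits of the point. A reader might infer that the trial will miss cardiac signals, or that the cardiovascular counts will certainly be too low. The documents support neither. The events are reported elsewhere, and an undercount needs three things that the documents do not establish: that sites report such findings as adverse events, that these code outside the two SOCs, and that the subject has no other qualifying event.

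The reply does not repair the table itself. Pulse thresholds do not show relatedness, seriousness or discontinuation. The SOC tables do, but with the events spread over several classes. The arrhythmia mark does not reach blood-pressure events. The arrhythmia row carries no cardiovascular label and can be read as using the mark alone. On that reading a marked event outside the two SOCs would still be absent from the main rows.

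**Conclusion.** The point holds as a limitation of one descriptive summary and is worth a cheap correction. As written, the rule can only lower the pooled cardiovascular counts, and it makes them depend on how sites word an event. The size of any shortfall cannot be estimated from the documents. The one usable figure is about 1.7 points per missed subject in a planned Part I arm of about 60.

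The conclusion about missed events rests on one assumption from outside the documents: that MedDRA places at least some measured heart-rate, blood-pressure or ECG findings under Investigations or another class. The ambiguity about the arrhythmia row does not depend on that assumption, because it follows from the SAP text alone. The evaluation of cardiac safety as a whole is not put in doubt.

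**What to change.** In SAP section 6.11.1, define a cardiovascular adverse event as one that meets any of these conditions:

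1. It is coded to Cardiac disorders or Vascular disorders.
2. It is marked as a cardiac arrhythmia on the eCRF.
3. Its preferred term is on a prespecified list of heart-rate, blood-pressure and ECG terms, regardless of SOC.

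Use this definition in every row of the cardiovascular TEAE summary, and state that the arrhythmia row counts all eCRF-marked events, so that it agrees with the separate arrhythmia table. Blinded staff, without access to the interim cardiac results, should fix the list before the Part I analysis (SAP section 7.3). If the unpublished shells already hold such a list, a cross-reference is enough.

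The cost is a sentence or two in the SAP, a term list to maintain and minor programming. Cardiovascular counts may come out slightly higher than under the present rule.

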- To evaluate the efficacy of SCD-044 in the treatment of Palmoplantar Psoriasis as measured by Palmoplantar Physician Global Assessment (PPPGA) score

Exploratory Objectives:

- To examine the pharmacodynamic/pharmacokinetic (PK/PD) relationship between SCD-044 plasma concentrations and PASI response
- [REDACTED]
- [REDACTED]
- To evaluate the effect of SCD-044 on subject reported outcome of itching associated with Psoriasis
- To evaluate the effect of SCD-044 on Psoriatic Arthritis (PsA)-related Pain (Patient Assessment of Pain (PtA-P))
- To evaluate the effect of SCD-044 on blood-based biomarkers.

Design:

Subjects in this randomized, double-blind, placebo controlled, parallel-group, multiple-center study will be assigned to treatment with the investigational products or placebo control according to a randomization scheme and titration schedule:

- **Part I:** 16 weeks: Subjects will be randomized to placebo, Low dose [REDACTED] Intermediate dose [REDACTED] or High dose [REDACTED] of SCD-044 [REDACTED]
[REDACTED]
[REDACTED]
[REDACTED]
[REDACTED] to assess primary and secondary endpoints at 16 weeks

Part II: Week 16 to Week 28:

At Week 16, subjects initially randomized to a treatment group will be re-randomized or discontinued from the study based on the PASI response as follows:

- Subjects initially randomized to placebo with a response of:

[REDACTED] will be re-randomized to Intermediate dose, High dose, [REDACTED]
[REDACTED]
[REDACTED] will be re-randomized to Intermediate dose or High dose [REDACTED]
[REDACTED]

- Subjects originally randomized to Low dose and Intermediate dose arms with a response of:

[REDACTED] will be switched to High dose [REDACTED]
[REDACTED]

[REDACTED] will remain on their assigned dosing regimen

- Subjects originally randomized to High dose arm with a response of:

[figure not shown]
[REDACTED]
[REDACTED] will remain on their assigned dosing regimen

Re-randomized subjects continuing in the study will stay on their assigned dosing regimen until the end of Part II (Week 28). [REDACTED]

[REDACTED]

[REDACTED]

- **Part III:** Week 28 to Week 52: Subjects with a response of [REDACTED] at Week 28 will be discontinued from the study. Subjects with a response of [REDACTED] at Week 28 will continue their existing dosing regimen until the end of Part III.

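### Adverse events with an onset date that could fall on either side of Week 16 always go to Part I, so SCD-044 events in former placebo subjects can be counted under placebo

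*SAP*

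**What the plan says.** SAP 6.11.1 assigns adverse events to study parts by onset date. When the date is known, "AEs that start on or after the date of the first Part II dose will be assigned to the Parts II/III", and earlier events belong to Part I. When a partial date leaves "ambiguity whether the AE starts in Part I or Part II, it will be assigned to Part I". No condition refers to a change of treatment.

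The protocol (Synopsis, Design; Section 3) changes treatment at Week 16. Depending on their response, placebo subjects "will be re-randomized to Intermediate dose or High dose", or are re-randomized among these two doses and a further option that is blacked out. Low- and intermediate-dose subjects in one response category "will be switched to High dose"; the others keep their dose. The groups for post-Week 16 data in SAP 6.1.1 include Placebo/SCD-044 combinations but no group that stays on placebo.

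SAP 6.11.1 presents adverse events in three ways. The first is "For events in Part I only, using Part I treatment groups", the second covers Parts II to IV by the later safety groups, and the third is "For the entire study using only the subjects who stayed on the same treatment throughout the study".

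The same section handles two other gaps cautiously. An event with an unknown or partial start date counts as treatment-emergent unless the available dates rule that out. For causality, "In case the relatedness was not assessed, the most conservative result (related) will be chosen for the analysis".

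**The concern.** Part I is the only placebo-controlled period, so its adverse event tables carry the comparison of SCD-044 with no drug. An event that began in the first days on SCD-044, but whose day of onset was not recorded, is charged to placebo when the subject came from the placebo arm. It also leaves the Part II column for the treatment actually being taken.

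The affected window overlaps Weeks 16, 17 and 18, for which SAP 6.11.1 plans a separate Part II table. For these subjects the rule runs in the opposite direction to the section's own rules for treatment-emergence and relatedness, and no reason is given.

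**Working it through.** The documents give no expected adverse event rate and no expected number of partial dates, so there is no stated figure to reproduce. The check traces one event through the tables and then bounds its effect.

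**Where an ambiguous event is counted, by type of subject**

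- Placebo to SCD-044: counted under placebo in Part I. If it began after the switch, the treatment is wrong, and the Placebo/SCD-044 column loses it.
- Low or intermediate to high: counted under the lower dose in Part I. If it began after the switch, the dose is wrong, but the event remains in the SCD-044 Any Dose column of the Part I table.
- Same dose throughout: counted under the same dose. The period may be wrong; the treatment is not.

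**Whether another planned output corrects it.** The whole-study presentation leaves out everyone who switched. Protocol 9.7 plans a summary by actual dose at onset. That summary is not among the three presentations in SAP 6.11.1, and it would need the same missing date.

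**Largest effect of one subject**

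- Arm size: 240 subjects at 1:1:1:1 (Protocol 4.1) gives 240/4 = 60. Effect on placebo Part I incidence: 1/60 = 1.7 points.
- Placebo/SCD-044 group size: not stated, so 20 to 30 is assumed. An equal split of all 60 into two groups gives 60/2 = 30; a split of 40 gives 40/2 = 20. Effect: 1/30 = 3.3 points to 1/20 = 5.0 points.
- Example with 4 true cases in the group: 4/20 = 20.0% becomes 3/20 = 15.0%, or 4/30 = 13.3% becomes 3/30 = 10.0%.

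These are upper limits, because SAP 6.11.1 counts a subject once per preferred term (or system organ class) and treatment. A subject who already has that term in the same column adds nothing.

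**Effect on display.** SAP 6.11.1 plans a table of events reaching 2% in any group. A term seen in a single subject would qualify in a Part II group of 20 to 30 (3.3% to 5.0%). Moved to placebo it stands at 1.7% and does not qualify, although it stays in the table of all treatment-emergent events.

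**How often the rule picks the wrong treatment for placebo switchers.** Suppose only the day is missing and the switch falls on day d of a 30-day month, each day equally likely. The share of the month on SCD-044 is s = (31 − d)/30, with average 465/900 = 0.517. If the event rate on drug is h times that on placebo (assumed), the chance that an ambiguous event began on drug is h·s/(h·s + 1 − s). Averaged over d, this is 52%, 58%, 63% and 69% for h = 1, 1.5, 2 and 3.

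**Illustration with assumed counts.** Take true Part I cases of 1/60 on placebo and 4/60 in one active arm: risk difference 5.0 points, risk ratio 4.0.

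- One post-switch event moved into placebo only: 2/60 against 4/60, difference 3.3 points, ratio 2.0.
- One event added to each arm: 2/60 against 5/60, difference still 5.0 points, ratio 2.5.

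**The case against.** A reader might infer that the rule favours SCD-044 as a whole. The documents do not support that. The rule is the same in all four arms, and three are active. Ambiguous events in active subjects also go to Part I, where they raise the active columns and the Any Dose column. If each arm gains equally, the risk difference does not move. For subjects moved to the high dose, the rule flatters that dose relative to the lower ones, while the event still counts against SCD-044 in the placebo-controlled table. The direction is clear only for former placebo subjects. This objection stands and sets the limits of the point.

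Exposure to the problem is also limited. Onset date is among the details to be documented for each adverse event (Protocol 5.9, 10.1), subjects keep diaries, and events are reviewed at Visits 10, 14 and 15. No event is lost; it stays treatment-emergent and is listed. That argues for a small effect, not for the rule.

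The SAP uses the word conservative only for missing relatedness and promises nothing similar for part assignment. So this is a difference in direction between neighbouring rules, not a contradiction.

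Finally, a different rule for placebo switchers has a cost. It sends some events that truly began on placebo to Part II, while same-dose subjects keep theirs in Part I, which lowers placebo relative to active. This is fair, and it is why the fix needs a sensitivity table.

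**Conclusion.** The point holds for subjects who move from placebo to SCD-044. For them the rule can attribute drug events to placebo in the only placebo-controlled safety table and remove them from the Part II column, and none of the three planned presentations recovers them. On the assumptions above, it chooses the wrong treatment for these subjects at least as often as the right one.

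The size is at most 1.7 points of placebo incidence per affected subject, and at most 3.3 to 5.0 points in a Part II group of 30 to 20. Those group sizes are assumed, because part of the re-randomization scheme is blacked out and SAP 6.2 also mentions non-responders discontinued after Part I. The number of partial dates spanning the switch is unknown, probably small, and could be zero. This is an inexpensive improvement to a convention. It does not show that the safety comparison is biased overall.

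**What to change.** In SAP 6.11.1:

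- For subjects who switched from placebo to SCD-044, assign an ambiguous event to Parts II/III unless its stop date, or the visit at which it was first reported, shows that it began before the first Part II dose.
- For subjects whose treatment did not change, keep the Part I rule.
- For subjects moved from the low or intermediate dose to the high dose, keep the Part I rule in the main tables and show the alternative in a sensitivity table.
- Footnote the number of ambiguous events by group, and add a sensitivity table with the opposite assignment.
- State which part holds events whose start date is wholly unknown. The SAP counts them as treatment-emergent but does not place them.

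Settle this before the Part I analysis (SAP 7.3), so that the choice is made without sight of results. The cost is a few SAP sentences, one programming condition and the sensitivity table. Incidence on SCD-044 in Part II may rise slightly. The date rule will no longer be identical across arms, and the sensitivity table shows how much that matters.
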